6.2. Preparation, Handling, and Accountability

For detailed information concerning the reconstitution, preparation, and infusion of the study drugs, refer to the Pharmacy Manual.

The investigator or designee must confirm appropriate temperature conditions have been maintained during transit for all study treatments received and any discrepancies are reported and resolved before use of the study treatment.

Only participants enrolled in the study may receive study treatment, and only authorized site staff may supply or administer study treatment. All study treatment must be stored in a secure, environmentally controlled, and monitored (manual or automated) area in accordance with the labeled storage conditions with access limited to the investigator and authorized site staff.

The investigator (or designee) is responsible for study treatment accountability, reconciliation, and record maintenance (ie, receipt, reconciliation, and final disposition records). Inventory and accountability records must be maintained and readily available for inspection by the study monitor and are open to inspection at any time by any applicable regulatory authorities. The investigator or designee must maintain records that document:

- Delivery of study drugs to the study site.
- Inventory of study drugs at the site.
- Participant use of the study drugs including vial counts from each supply dispensed.
- Lot numbers and/or vial numbers (as applicable) of study drugs used to prepare the infusion solution.

The investigational product must be used only in accordance with the Protocol. The investigator will also maintain records adequately documenting that the participants were provided the specified study drug. These records should include dates, quantities, and any available batch or serial numbers or unique code numbers assigned to the investigational product and study participants.

Completed accountability records will be archived by the site. The investigator or designee will be expected to collect and retain all used, unused, and partially used containers of the study drugs until verified by the study monitor (unless otherwise agreed to by the sponsor). At the conclusion of the study, the investigator or designee will oversee shipment of any remaining study drugs back to the sponsor or its designee for destruction according to institutional SOPs. If local procedures mandate on-site destruction of investigational supply, the site should (where local procedures allow) maintain the investigational supply until the study monitor inspects the accountability records in order to evaluate compliance and accuracy of accountability by the

investigative site. At sites where the study drugs are destroyed before monitor inspection, the monitors rely on documentation of destruction per the site SOP.

Further guidance and information for the final disposition of unused study treatments are provided in the Pharmacy Manual.

6.3. Measures to Minimize Bias: Randomization and Blinding

All participants will be centrally assigned to study treatment using an IRT. Full details will be provided in the IRT Manual.

Study treatment will be dispensed at the study visits summarized in the SoA (see [Table 3](#)).

Centralized randomization numbers within each stratum will be created for treatment assignment. Participants will be assigned to study treatment in accordance with the randomization schedule. Participants, investigators, the sponsor, and the study team will be blinded to treatment assignment. See emergency unblinding procedures in [Section 9.6](#).

A sponsor statistician who is not part of the study team will be unblinded and may provide summary aggregated data by treatment group to the DSMB, but individual participant data will remain blinded.

6.4. Study Treatment Compliance

Compliance with study treatment administration will be calculated by the sponsor based on study drug accountability and infusion records documented by the site staff and monitored by the sponsor/designee.

6.5. Dose Modifications

6.5.1. Criteria and Procedures for Dose Interruptions and Adjustments of Study Drugs

Individual decisions regarding dose modifications of study treatment should be made using clinical judgment in consultation with the medical monitor (whenever possible), taking into account relatedness of the AE to the study treatment and the participant's underlying condition. Adverse events that have a clear alternative explanation, or transient (≤ 72 hours) abnormal laboratory values without associated clinically significant signs or symptoms, may be exempt from dose-interruption rules.

Safety concerns should be discussed with the sponsor immediately upon occurrence or awareness to determine if the participant should continue or discontinue study treatment.

Dose modification of study drugs (INCAGN02385, INCAGN02390, and retifanlimab) is not permitted. If a dose-interruption is necessary for management of treatment-related TEAEs, study drugs will be reinitiated at the starting dose.

Treatment with study drugs may be interrupted up to 4 weeks (28 days) to allow for resolution of toxicity, unless a longer interruption is approved by the sponsor. All study drugs should be interrupted at the same time for the same duration. Participants may resume treatment if no medical condition or other circumstance exists that, in the opinion of the investigator, would make the participant unsuitable for further participation in the study. The treating investigator

should contact the sponsor to discuss the case of any participant whose treatment has been delayed for more than 28 days before restarting the study treatment.

Given the Q2W infusion schedule for INCAGN02385/placebo and INCAGN02390/placebo, if Day 15 infusions had to be delayed because of toxicity, the next dose of INCAGN02385/placebo and INCAGN02390/placebo can be resumed once the toxicity resolves as per protocol guidance:

- If treatment is restarted < 2 weeks from the last treatment visit, resume INCAGN02385/placebo plus INCAGN02390/placebo only (that would be considered Day 15), then the subsequent treatment visit should occur 2 weeks later with the triplet (including retifanlimab) and continue per protocol schedule.
- If treatment is restarted \geq 2 weeks from last treatment visit, proceed with the triplet combination (ie, omit the Day 15 dose of the doublet INCAGN02385/placebo plus INCAGN02390/placebo) and continue per study schedule.

Decisions regarding these dose interruptions and restart of study drugs will be made according to Section 6.5.1.1 for non-irAEs, Section 6.5.2 for suspected infusion reactions and Section 6.5.3 for irAEs and, when needed, jointly by the investigator and medical monitor on a case-by-case basis.

Dose interruptions are permitted in the case of medical or surgical events (eg, elective surgery, unrelated medical events). In such a case, study treatment should resume within 4 weeks of the scheduled interruption, unless otherwise discussed with the sponsor. Delayed study treatment administration in the case of logistical reasons not related to study therapy (eg, participant vacation, holidays) is permitted. In such a case, study treatment should resume within 3 to a maximum of 7 days of the scheduled interruption, unless otherwise discussed with the sponsor.

For participants who have active, confirmed (positive results from an approved COVID-19 test) or presumed (test pending/clinical suspicion) SARS-CoV2 infection, guidelines in Appendix C should be followed.

If treatment is permanently discontinued for toxicity, all 3 study drugs must be discontinued and the EOT visit should be conducted.

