Adherence to the study design requirements, including those specified in the SoA, is essential and required for study conduct.

Figure 1: Study Design Schema

[figure not shown]

Table 3: Schedule of Activities

Visit Day (Range)	Screening	Treatment						EOT	Safety Follow-Up	Survival Follow-Up	Notes
	Days –28 to –1	Cycle 1			Cycle 2+		Q8W (± 7 d)		EOT + 30 and 90 days (± 7 d)	Q12W (± 14 d)	
		Day 1	Day 8 (± 2 d)	Day 15 (± 2 d)	Day 1 (± 3 d)	Day 15 (± 2 d)					
Administrative procedures											
Informed consent	X										See Section 8.1.1 for details.
Contact IRT	X	X		X	X	X		X	X		See Section 8.1.3 for details.
Inclusion/exclusion criteria	X	X									See Section 5 for details.
Demographics and general and disease medical history	X										See Section 8.1.5 for details.
HPV p16 testing	X										Participants with primary oropharyngeal tumors must have known HPV status (determined locally; otherwise, request central testing per sponsor) prior to randomization. See Section 5.1 for details.
Prior/concomitant medications	X	X	X	X	X	X		X	X		Section 8.1.6 for details.
Administer retifanlimab		X			X						Retifanlimab administered on Day 1 of each cycle (Q4W). See Section 6.1 for details.
Administer INCAGN02385/placebo		X		X	X	X					Administered Q2W of each cycle. See Section 6.1 for details.
Administer INCAGN02390/placebo		X*		X	X	X					*Following completion of the Cycle 1 Day 1 INCAGN02390/placebo infusion, participants will be observed at the study site for 4 hours per Section 6.5.2.
Distribute reminder card		X	X	X	X	X		X	X		See Section 8.1.4 for details.
Safety assessments											
AE assessments	X	X	X	X	X	X		X	X		See Section 8.3.1 for details.
Physical examination/body weight/height	X	X	X	X	X	X		X	X		Complete physical exam at screening; targeted physical thereafter. Height at screening only. Body weight at screening and Day 1 of each cycle. See Section 8.3.2 for details.

Table 3: Schedule of Activities (Continued)

Visit Day (Range)	Screening	Treatment						EOT	Safety Follow-Up	Survival Follow-Up	Notes
	Days –28 to –1	Cycle 1			Cycle 2+		Q8W (± 7 d)		EOT + 30 and 90 days (± 7 d)	Q12W (± 14 d)	
		Day 1	Day 8 (± 2 d)	Day 15 (± 2 d)	Day 1 (± 3 d)	Day 15 (± 2 d)					
Safety assessments (continued)											

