6. STUDY TREATMENT

6.1. Study Treatments Administered

Table 8 presents the study treatment information.

Table 8: Study Treatment Information

	Study Treatment 1	Study Treatment 2	Study Treatment 3
Study treatment name:	Retifanlimab (INCMGA00012)	INCAGN02385/placebo	INCAGN02390/placebo
Dose formulation:	Solution for infusion	Solution for infusion	Solution for infusion
Unit dose strength(s)/ dose level(s):	25 mg/mL in a glass vial for single use Dose level: 500 mg Q4W	50 mg/mL Dose level: 350 mg Q2W	50 mg/mL Dose level: 400 mg Q2W
Route of administration	IV (30-minute infusion with filter followed by 10-minute flush)	IV (30-minute infusion with filter followed by 10-minute flush)	IV (30-minute infusion with filter followed by 10-minute flush)
Packaging and labeling	Study drug will be provided in a vial. Each vial will be labeled as required per country requirement.	Study drug will be provided in a vial. Each vial will be labeled as required per country requirement.	Study drug will be provided in a vial. Each vial will be labeled as required per country requirement.
Status of treatment in participating countries:	Investigational	Investigational	Investigational

The order of administration of study drugs on Day 1 of each cycle should be retifanlimab, followed by INCAGN02385/placebo, followed by INCAGN02390/placebo.

The order of administration of study drugs on Day 15 of each cycle should be INCAGN02385/placebo followed by INCAGN02390/placebo; retifanlimab is not administered on Day 15.

As outlined in Table 8, infusions are 30 minutes each with a 10-minute flush followed by the next infusion. For additional details regarding infusion of study drugs, refer to the Pharmacy Manual.

Study treatment will be administered for up to 2 years, or until discontinuation criteria are met (see Section 7.1.1). Study treatment may be administered \pm 3 days of the scheduled Day 1 for each cycle (except for Cycle 1 Day 1, on which the study treatment will be administered specifically on Day 1) and \pm 2 days of the scheduled Day 15 for each cycle. INCAGN02385/placebo and INCAGN02390/placebo doses should not be administered < 12 days apart.

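### The Day 15 restart rule in Protocol 6.5.1 does not say which visit its 2 weeks are counted from; read literally, one branch cannot be reached and Day 15 delays of 3 to 13 days bring retifanlimab forward of its 4-week schedule

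*Protocol*

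**What the plan says.** The rule is in Protocol 6.5.1. It applies "if Day 15 infusions had to be delayed because of toxicity" and has two branches.

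- First branch: "If treatment is restarted < 2 weeks from the last treatment visit, resume INCAGN02385/placebo plus INCAGN02390/placebo only (that would be considered Day 15". The next visit, with retifanlimab added, follows 2 weeks later.
- Second branch, for a restart at or beyond "2 weeks from last treatment visit, proceed with the triplet combination": the Day 15 doublet is omitted, and dosing continues on the study schedule.

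The schedule that the rule has to fit is set elsewhere in the Protocol.

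- Table 3: "Retifanlimab administered on Day 1 of each cycle (Q4W", that is, every 28 days.
- Section 6.1 on the mid-cycle visit: "retifanlimab is not administered on Day 15".
- Section 6.1 on windows: dosing is allowed within plus or minus "3 days of the scheduled Day 1 for each cycle" (Cycle 1 Day 1 is fixed), and within plus or minus 2 days of the scheduled Day 15.
- Section 6.1 on spacing: "INCAGN02385/placebo and INCAGN02390/placebo doses should not be administered < 12 days apart". No minimum interval is given there for retifanlimab.

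Neither document defines the last treatment visit.

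**The concern.** The rule exists for one situation: Day 15 was due and was not given. The last visit at which the participant received drug is then Day 1, which is already 14 days before the scheduled Day 15. A 2-week threshold counted from Day 1 has therefore been reached before any delay begins, so it cannot separate short delays from long ones.

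The practical consequence is a dosing instruction, used straight after toxicity, that two careful sites can apply differently. One could give retifanlimab at the restart; the other could give the doublet and hold retifanlimab for 2 more weeks. Retifanlimab is given in all three groups and is the only active drug in TG1, so its timing should not depend on how a site reads an undefined phrase.

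**Working it through.** This is calendar arithmetic. The Protocol states no figure to reproduce.

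**Inputs.** Scheduled Day 15 is 14 days after Day 1. The retifanlimab interval is 28 days, with a Day 1 window of plus or minus 3 days, so 25 to 31 days. The Day 15 window is plus or minus 2 days. The doublet minimum spacing is 12 days. The threshold in 6.5.1 is 2 weeks, or 14 days. Let d be the number of days by which Day 15 is late.

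**Reading A: count from the last visit at which drug was given (Day 1).**

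- Gap at restart = 14 + d. For any d of 1 or more the gap is at least 15 days, so the second branch always applies.
- The first branch needs a gap under 14 days. With the 12-day minimum, only 12 or 13 days qualify, and that is an early Day 15 inside its window, not a delayed one.
- Retifanlimab is given at the restart, so its interval is 14 + d days.

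**Reading B: count from the missed Day 15.**

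- For d under 14 the first branch applies. The doublet is given at 14 + d days and retifanlimab 14 days later, so the retifanlimab interval is 14 + d + 14 = 28 + d days.
- For d of 14 or more the second branch applies, and the interval is 14 + d days.

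| Delay d (days) | Reading A: retifanlimab interval (days) | Against 25 to 31 days | Reading B: retifanlimab interval (days) |
|---|---|---|---|
| 3 | 17 | early | 31 |
| 10 | 24 | early | 38 |
| 11 | 25 | inside, but under 28 | 39 |
| 13 | 27 | inside, but under 28 | 41 |
| 14 | 28 | on schedule | 28 |
| 17 | 31 | on schedule | 31 |
| 18 | 32 | late | 32 |

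The table starts at d = 3 because a slip of 1 or 2 days is still a permitted Day 15 under Section 6.1.

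**Difference between the readings.** For d from 3 to 13, (28 + d) − (14 + d) = 14 days. From d = 14 onward they agree.

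**Edge case.** Suppose Day 15 is counted from a nominal Day 1 that was dosed 3 days late. Scheduled Day 15 is then 11 days after the actual dose, and delays of 1 or 2 days give gaps of 12 or 13 days, which reach the first branch. Those delays lie inside the Day 15 window. At d = 3 the gap is 11 + 3 = 14 days, and the second branch applies again. SAP 4.1.5, which ties the actual Day 1 of later cycles to retifanlimab administration, also argues against counting this way.

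**Which reading the text supports.** Protocol 8.6 groups scheduled visits at which dosing is held for toxicity with unscheduled visits. This makes it hard to call a held Day 15 a treatment visit and favors Reading A. The rationale for this change in the Amendment 2 summary (Appendix D, item 12) describes a 2-week limit on the Day 15 delay itself, which favors Reading B. That entry is evidence of intent only; the operative text in 6.5.1 does not say it.

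**The case against.** The strongest reply is that Reading A is not what the sponsor meant. The amendment rationale measures the delay of Day 15, and on that basis both branches can be reached and no retifanlimab dose falls before 28 days. In addition, the second branch ends by telling sites to continue on the study schedule, which could be read as skipping Day 15 and waiting for the next scheduled Day 1; retifanlimab would then not be advanced at all. Section 6.5.1 also asks for consultation with the medical monitor whenever possible and provides for joint case-by-case decisions when needed. The IRT and Pharmacy Manuals, which are not available here, may settle the point.

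Much of this stands. The finding is an ambiguity with a literal reading that misfires, and it does not show that sites have dosed early. It does not remove the problem. Likely intent does not change the operative wording, and the second branch presents the triplet as what is given when treatment restarts: "proceed with the triplet combination (ie, omit the Day 15 dose of the doublet INCAGN02385/placebo plus INCAGN02390/placebo". Medical monitor input does not define the reference visit.

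Three stronger conclusions might be inferred, and the documents do not support them.

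- That every Day 15 delay advances retifanlimab. Even on Reading A, delays of 11 to 17 days stay within 25 to 31 days, and longer ones make it late.
- That a 1-day slip nearly doubles retifanlimab dosing for that interval. A 1-day slip is inside the Day 15 window, where Section 6.1 gives the doublet only.
- That the rule confounds TG2 or TG3 against TG1. It applies identically in all three blinded groups, since TG1 also has Day 15 placebo infusions, and neither document gives delay rates by group.

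**Conclusion.** The concern holds as an internal inconsistency in a dosing rule. Read literally, the doublet-only branch of Protocol 6.5.1 cannot be reached by a delayed Day 15. Out-of-window delays under 2 weeks (3 to 13 days) then give retifanlimab 17 to 27 days after the previous dose. For delays of 3 to 10 days the interval is 17 to 24 days, outside the range that the Day 1 window allows. Delays of 14 to 17 days are on schedule and longer ones are late. The literal result conflicts with the 4-weekly schedule in Table 3 and with Section 6.1, which keeps retifanlimab off Day 15. The alternative reference visit removes that conflict, and the 14-day difference between the readings measures the ambiguity.

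This rests on three assumptions: that the last treatment visit means the last visit at which drug was given, that the second branch means retifanlimab at the restart itself, and that dosing within 2 days of the scheduled Day 15 is not a delay. How long a delay can run without sponsor approval also depends on where the 28-day interruption limit starts: up to 14 days late if counted from Day 1, up to 28 if counted from the missed Day 15. A 14-day delay is allowed either way. No effect on the treatment comparison is claimed.

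**What to change.** Reconcile Protocol 6.5.1 with Section 6.1 and Table 3.

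- State which visit the 2 weeks are counted from, so that both branches can be reached.
- State whether a slip inside the Day 15 window counts as a delay under this rule.
- State how the 4-week retifanlimab interval and the visit windows apply after a delay. Reading B needs this too: delays of 4 to 13 days give intervals of 32 to 41 days, beyond the nominal 31.
- Check that the IRT follows the same rule, since Table 3 has sites contact it at Day 15 visits.

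Which rule is clinically appropriate is for the sponsor to decide; none is proposed here. The cost is a clarification letter or amendment wording and an IRT check, with no added participants, visits or procedures.

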6.5.1.1. Procedures for Participants Exhibiting Drug-Related, Non-Immune-Related Adverse Events

The guidance presented in Table 9 should be followed as best practice for decisions regarding management of non-irAEs.

Table 9: Management Guidelines for Drug-Related, Non-Immune-Related Adverse Events

CTCAE Grade	Suggested Modification for INCAGN02385, INCAGN02390, and Retifanlimab
Grade 1 or Grade 2	Continue treatment at the discretion of the investigator.
Grade 3	
 • Withhold treatment until resolution to \leq Grade 1. • Permanently discontinue study treatment after third occurrence of toxicity, unless approved by the medical monitor to continue.
Grade 4	Permanently discontinue study treatment or discuss with medical monitor if treatment algorithm for CTCAE Grade 3 events (above) is appropriate.

6.5.2. Management of Suspected Infusion Reactions

Immunotherapies have been associated with the occurrence of infusion reactions. Infusion or hypersensitivity reactions may be observed with administration of any foreign protein.

Premedication with an antipyretic (eg, acetaminophen/paracetamol or ibuprofen) and a histamine blocker (eg, diphenhydramine) should be considered for participants who have had previous systemic reactions to protein product infusions or when recommended by institutional policy. Routine prophylaxis is not required.

Participants should be monitored closely during the study drug infusion period and are required to remain at the study site on Cycle 1 Day 1 for safety observation for potential IRRs for at least 4 hours after completion of the final infusion (INCAGN02390/placebo). From Cycle 2 onwards, participants may be required to stay at the investigator's discretion.

Guidelines for management of suspected infusion reactions are provided in [Table 10](#).

Table 10: Guidelines for Management of Suspected Infusion Reactions

Grade	Description	Treatment	Subsequent Infusions
1	Mild reaction; infusion interruption not indicated; intervention not indicated.	Monitor vital signs closely until medically stable.	Premedication with an antipyretic (eg, acetaminophen/paracetamol) and a histamine blocker should be considered for participants who have had previous systemic reactions to protein product infusions or when recommended by institutional policy.
2	Requires infusion interruption but responds promptly to symptomatic treatment (eg, antihistamines, NSAIDs, narcotics, IV fluids); prophylactic medications indicated for ≤ 24 hours.	
First occurrence: Stop infusion and initiate appropriate medical measures (eg, IV fluids, antihistamines, NSAIDs, antipyretics, narcotics) per institutional preferences.
 
Monitor vital signs until medically stable.
 
If symptoms resolve within 1 hour, infusion may be resumed at 50% of the original infusion rate.
 
Subsequent occurrences (after recommended prophylaxis): Permanently discontinue study treatment.
	
Premedicate at least 30 minutes before infusion with antihistamines (eg, diphenhydramine 50 mg PO) and an antipyretic (eg, acetaminophen/paracetamol 500-1000 mg PO).
 
Additional supportive measures may be acceptable (per institutional preference) but should be discussed with medical monitor.
 
Next infusion should start at 50% of the original infusion rate. If no reaction, rate of infusion can be increase by 25% every 15 minutes until a rate of 100% has been reached. Subsequent infusions can begin at 100%.

3 or 4	
Grade 3: Prolonged (ie, not rapidly responsive to symptomatic medication and/or brief interruption of infusion); recurrence of symptoms following initial improvement; hospitalization indicated for other clinical sequelae (eg, renal impairment, pulmonary infiltrates).
 
Grade 4: Life-threatening; pressor or ventilatory support indicated.
	
Stop infusion and initiate appropriate medical therapy (eg, IV fluids, antihistamines NSAIDs, antipyretics, narcotics, oxygen, pressors, epinephrine, corticosteroids) per institutional preferences.
 
Monitor vital signs frequently until medically stable.
 
Hospitalization may be indicated.
	Permanently discontinue study treatment.

Note: Per NCI CTCAE v5.0, appropriate resuscitation equipment should be available at the bedside and a physician readily available during the period of study treatment administration ([NCI 2017](#)).

